2. OBJECTIVES

2.1. Primary objective

- To assess the immunological response to hepatitis B antigen, in terms of antibody concentrations ≥ 100 mIU/ml, one month after the single challenge dose of the HBV vaccine in subjects 14-15 years of age, previously vaccinated with four doses of *Infanrix hexa* in the first two years of life.

[figure not shown]
Refer to Section 10.1 for the definition of the primary endpoint.

2.2. Secondary objectives

- To assess the persistence of anti-HBs antibodies, in terms of seroprotection status and antibody concentrations, in subjects 14-15 years of age, previously vaccinated with four doses of *Infanrix hexa* in the first two years of life.
- To assess the immunological response to hepatitis B antigen, in terms of anamnestic response, one month after the single challenge dose of the HBV vaccine in subjects 14-15 years of age, previously vaccinated with four doses of *Infanrix hexa* in the first two years of life.
- To assess the immunological response to the hepatitis B antigen, in terms of seroprotection status and antibody concentrations, one month after the single challenge dose of the HBV vaccine in subjects 14-15 years of age, previously vaccinated with four doses of *Infanrix hexa* in the first two years of life.
- To evaluate the safety and reactogenicity of a single challenge dose of HBV vaccine (*Engerix-B Kinder*) in terms of solicited symptoms (local and general), unsolicited symptoms and serious adverse events (SAEs).

Refer to Section 10.2 for the definition of the secondary endpoints.

3. STUDY DESIGN OVERVIEW

N: Number of subjects planned to be enrolled

* Pre-vaccination: Blood sampling before the administration of the single HBV vaccine challenge dose

** Post-vaccination: Blood sampling one month after the administration of the single HBV vaccine challenge dose

Protocol waivers or exemptions are not allowed with the exception of immediate safety concerns. Therefore, adherence to the study design requirements, including those specified in the outline of study procedures (Section 5.5), are essential and required for study conduct.

- Experimental design: Phase IV, open-label, non-randomised, multi-centric, single-country study with a single group.
- Duration of the study: the intended duration of the study, per subject, will be approximately one month. The study will have a single epoch as follows:
 - Epoch 001: Primary starting at Visit 1 (Day 0) and ending at Visit 2 (Month 1).
- Study groups: the details are presented below in [Table 1](#).

Table 1 Study groups and epochs foreseen in the study

Study groups	Number of subjects	Age (Min/Max)	Epochs
			Epoch 001
HBV Group	300	14 years – 15 years	x

The treatment group details are provided in [Table 2](#).

Table 2 Study groups and treatment foreseen in the study

Treatment name	Vaccine name	HBV Group
Engerix-B Kinder	HBV	•

- Control: uncontrolled
- Vaccination schedule: A single dose of HBV vaccine will be administered to all subjects, who were previously primed and boosted with four doses of *Infanrix hexa* in the first two years of life.
- Treatment allocation: non-randomised
- Blinding: Refer to [Table 3](#).

Table 3 **Blinding of study epochs**

Study Epochs	Blinding
Epoch 001	open

- Sampling schedule: Blood samples will be taken from each subject at the following time-points:
 - Pre-vaccination: at Visit 1, before the administration of the single challenge dose of HBV vaccine.
 - Post-vaccination: at Visit 2, approximately one month after the single challenge dose of HBV vaccine.
- Type of study: self-contained
- Data collection: Electronic Case Report Form (eCRF).

4. STUDY COHORT

4.1. Number of subjects/centres

Approximately 300 children aged 14-15 years will be enrolled in this study. They should have received four doses of *Infanrix hexa* with the three primary vaccination doses received by 9 months of age and the booster dose received between 11 and 18 months of age as part of routine vaccination practice in Germany.

Parents/Legally Acceptable Representative(s) [LAR(s)] of these children will be contacted and their children will be invited to participate in this challenge dose study.

Refer to Section 10.3 for a detailed description of criteria used to estimate the sample size.

Overview of the recruitment plan

- The study will be conducted at multiple centres in Germany.
- Enrolment is expected to be completed within a period of approximately six months.
- The study duration per subject will be approximately one month.
- The follow-up of recruitment of subjects into the study will be performed using GSK Biologicals' central randomisation system on Internet (SBIR).
- The recruitment will be monitored by the site monitor.

4.2. Inclusion criteria for enrolment

Deviations from inclusion criteria are not allowed because they can potentially jeopardize the scientific integrity of the study, regulatory acceptability or subject safety. Therefore, adherence to the criteria as specified in the protocol is essential.

All subjects must satisfy ALL the following criteria at study entry:

- Subjects' parent(s)/Legally Acceptable Representative(s) [LAR(s)] who, in the opinion of the investigator, can and will comply with the requirements of the protocol (e.g. completion of the diary cards, return for follow-up visits).
- Written informed consent obtained from the parent(s)/LAR(s) of the subject prior to performance of any study specific procedure.
- In addition to the informed consent that will be signed by the parents/LAR(s), written informed assent of the subject will be sought.
- A male or female between the ages of 14 to 15 (from and including the 14th birthday, up to but excluding the 16th birthday) at the time of vaccination.
- Healthy subjects as established by medical history and clinical examination before entering into the study.
- Subjects with documented evidence of previous vaccination with four consecutive doses of *Infanrix hexa* as part of routine vaccination in Germany: three doses of primary vaccination received by 9 months of age and one booster dose received between 11 and 18 months of age.
- Female subjects of non-childbearing potential may be enrolled in the study.
 - Non-childbearing potential is defined as pre-menarche, current tubal ligation, hysterectomy or ovariectomy.

Please refer to the [glossary of terms](#) for the definition of menarche.

- Female subjects of childbearing potential may be enrolled in the study, if the subject:
 - has practiced adequate contraception for 30 days prior to vaccination, and
 - has a negative pregnancy test on the day of vaccination, and
 - has agreed to continue adequate contraception during the entire treatment period and for 2 months after completion of the vaccination series.

Please refer to the [glossary of terms](#) for the definition of adequate contraception.

4.3. Exclusion criteria for enrolment

Deviations from exclusion criteria are not allowed because they can potentially jeopardize the scientific integrity of the study, regulatory acceptability or subject safety. Therefore, adherence to the criteria as specified in the protocol is essential.

The following criteria should be checked at the time of study entry. If ANY exclusion criterion applies, the subject must not be included in the study:

- Child in care.

Please refer to the [glossary of terms](#) for the definition of child in care.

- Use of any investigational or non-registered product (drug or vaccine) other than the study vaccine during the period starting 30 days before the dose of study vaccine (Day -29 to Day 0), or planned use during the study period.
- Any medical condition that in the judgment of the investigator would make intramuscular injection unsafe.
- Chronic administration (defined as more than 14 days in total) of immunosuppressants or other immune-modifying drugs during the period starting six months prior to the vaccine dose. For corticosteroids, this will mean prednisone \geq 0.5 mg/kg/day (for paediatric subjects), or equivalent. Inhaled and topical steroids are allowed.
- Administration of long-acting immune-modifying drugs at any time during the study period (e.g. infliximab).
- Planned administration/administration of a vaccine not foreseen by the study protocol in the period starting 30 days before the dose and ending 30 days after the dose of HBV vaccine administration with the exception of tetanus toxoid, reduced diphtheria toxoid and acellular pertussis (dTpa) vaccine, which can be given as part of routine vaccination practice. Seasonal or pandemic influenza vaccine can be given at any time during the study, and according to the Summary of Product Characteristics and national recommendations.
- Concurrently participating in another clinical study, at any time during the study period, in which the subject has been or will be exposed to an investigational or a non-investigational vaccine/product (pharmaceutical product or device).
- Evidence of previous hepatitis B booster vaccination since administration of the fourth dose of *Infanrix hexa* booster in the second year of life.
- History of or intercurrent hepatitis B disease.
- Hepatitis B vaccination at birth.
- Any confirmed or suspected immunosuppressive or immunodeficient condition, based on medical history and physical examination (no laboratory testing required).
- Family history of congenital or hereditary immunodeficiency.
- History of any reaction or hypersensitivity (hypotone-hyperresponsiveness reaction) likely to be exacerbated by any component of the vaccine.
- Major congenital defects or serious chronic illness including thrombocytopenia and bleeding disorders.
- History of any neurological disorders or seizures.
- Acute disease and/or fever at the time of enrolment.
 - Fever is defined as temperature \geq 37.5°C for oral, axillary or tympanic route, or \geq 38.0°C for rectal route.
 - Subjects with a minor illness (such as mild diarrhoea, mild upper respiratory infection) without fever may be enrolled at the discretion of the investigator.

- Acute or chronic, clinically significant pulmonary, cardiovascular, hepatic or renal functional abnormality, as determined by physical examination or laboratory screening tests.
- Administration of immunoglobulins and/or any blood products during the period starting 3 months before the dose of study vaccine or planned administration during the study period.
- Pregnant or lactating female.
- Female planning to become pregnant or planning to discontinue contraceptive precautions.

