10.4.3. According-to-protocol cohort for analyses of antibody persistence

The ATP cohort for analyses of antibody persistence will include all enrolled subjects:

- aged 14–15 years (from and including the 14th birthday up to but excluding the 16th birthday) at the time of enrolment.
- who have not received any additional dose of hepatitis B vaccine (or any other vaccine with this antigen component) other than the four doses of *Infanrix hexa* during the first two years of life.
- with no evidence of hepatitis B infection or disease (including anti-HBc at post-HBV challenge dose time point).
- for whom serological results are available at the pre-HBV challenge blood sampling time point.

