10.7. Analyses of immunogenicity

Analyses for antibody persistence

The analyses for antibody persistence will be performed on the ATP cohort for analyses of antibody persistence.

- Prior to the single dose of HBV vaccine:
 - Percentage of subjects with anti-HBs antibody concentrations ≥ 6.2 mIU/ml, ≥ 10 mIU/ml, ≥ 10 mIU/ml to < 100 mIU/ml, and ≥ 100 mIU/ml, with exact 95% CI will be calculated [[Clopper](#), 1934].
 - GMCs with 95% CI will be calculated for anti-HBs antibodies.
 - The distribution of anti-HBs antibody concentrations will be displayed using reverse cumulative curves (RCCs).

Response to challenge dose

The primary analyses will be based on the ATP cohort for analyses of immunogenicity. If, the percentage of vaccinated subjects with serological results excluded from the ATP cohort for analyses of immunogenicity is 5% or more, a second analyses based on the TVC will be performed to complement the ATP analyses.

- One month after the single challenge dose of HBV vaccine:
 - Percentage of subjects with anti-HBs antibody concentrations ≥ 6.2 mIU/ml, ≥ 10 mIU/ml and ≥ 100 mIU/ml, with exact 95% CI will be calculated [Clopper, 1934].
 - GMCs with 95% CI will be calculated for anti-HBs antibodies.
 - The distribution of anti-HBs antibody concentrations will be displayed using RCCs.
- The percentage of subjects with anti-HBs concentrations ≥ 6.2 mIU/ml, ≥ 10 mIU/ml, and ≥ 100 mIU/ml (with exact 95% CI) and GMCs at the post-HBV challenge dose time-point, in relation to their pre-challenge dose status (< 6.2 mIU/ml, < 10 mIU/ml, ≥ 10 mIU/ml) will be tabulated [Clopper, 1934].
- Percentage of subjects (with 95% CI) who mount an anamnestic response to the single challenge dose of HBV vaccine will be calculated overall and in relation to their pre-vaccination status (< 6.2 mIU/ml, < 10 mIU/ml, ≥ 10 mIU/ml) [Clopper, 1934].
- Post-challenge anti-HBs antibody concentrations as a function of pre-challenge concentrations, with regression line will be computed using linear regression method for ATP cohort for immunogenicity only. The model will include pre-challenge log transformed concentrations as regressor (independent or explanatory variable) and post-challenge log-transformed concentrations as an outcome (dependent or response) variable. Antibody concentrations observed at the pre-challenge dose time point will be presented graphically.

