9. CHANGES FROM PLANNED ANALYSES

The major changes from the protocol are,

- According-to-protocol cohort for analyses of antibody persistence defined in the protocol for the analysis of antibody persistence was removed from the SAP to reduce the number of cohorts used in the analysis. The analysis of persistence and response to challenge dose will be performed on the According-to-protocol cohort for analyses of immunogenicity. This change will not have significant impact on the analysis of persistence as no major difference in number of subjects expected between the ATP cohort for analysis of Immunogenicity and ATP cohort for analyses of antibody persistence.

Other changes include,

- The analysis for persistence and response to challenge dose is harmonized with respect to the cut-offs to consider.
 - The analysis to summarize the number and percentage of subjects between >10 mIU/mL and < 100 mIU/mL planned in the protocol was removed to be consistent with the endpoints of the study.
 - The analysis to summarize the post challenge dose response and anamnestic response stratified by the pre-challenge dose concentrations will be performed by considering the categories < 6.2 mIU/ml, ≥ 6.2 mIU/ml - < 10 mIU/ml, and ≥ 10 mIU/ml at pre-challenge dose time point.
- All the analysis of solicited and/or unsolicited adverse events will be performed for any, grade 3, by relationship to vaccination, and requiring medical attention to be consistent with the presentation of the adverse events summary.

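### Removing the persistence cohort from the SAP also removed the rule against extra hepatitis B doses, so a dose given after birth and before the first Infanrix hexa dose no longer excludes a subject from the persistence analysis

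*Protocol*

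**What the plan says.** Entry criteria. Protocol Section 4.2 asks for "Subjects with documented evidence of previous vaccination with four consecutive doses of" Infanrix hexa, three by 9 months and one at 11 to 18 months. It does not say that no other hepatitis B vaccine was given. Section 4.3 has two exclusions on earlier hepatitis B vaccination: "Hepatitis B vaccination at birth" and "Evidence of previous hepatitis B booster vaccination since administration of the fourth dose".

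Protocol analysis sets. Section 10.4.3 is broader than the entry criteria. Its persistence cohort takes only subjects "who have not received any additional dose of hepatitis B vaccine (or any other vaccine with this antigen component) other than the four doses", meaning the Infanrix hexa course in the first two years. Section 10.7 says where that cohort is used: "The analyses for antibody persistence will be performed on the ATP cohort for analyses of antibody persistence". The response to the challenge dose, including the primary endpoint, is assigned in the same section to the ATP immunogenicity cohort of Section 10.4.2, which has no additional-dose rule.

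SAP. Section 9 records that the persistence cohort "defined in the protocol for the analysis of antibody persistence was removed from the SAP to reduce the number of cohorts", and then that "The analysis of persistence and response to challenge dose will be performed on the According-to-protocol cohort for analyses of immunogenicity". The reason given is that the two cohorts should not differ much in size. The additional-dose rule is not mentioned.

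**The concern.** The objectives and the group label in every table describe subjects who had four doses of Infanrix hexa. Section 10.4.3 was the only place that turned this into a requirement of no other hepatitis B-containing dose at any time before the challenge. Once that cohort is gone, the persistence analysis depends on entry criteria that name two periods and leave at least one uncovered.

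Take a child given a monovalent hepatitis B dose a few weeks after birth and then four documented Infanrix hexa doses on schedule. That child satisfies Section 4.2, meets neither exclusion in Section 4.3, and would be counted in the percentages and GMCs reported as persistence after four doses. The plausible direction of error is upward, although the documents contain no data on it. What is at stake is whether the analysed set matches its label in a follow-up programme requested by the EMA.

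**Working it through.** **1. Is the history caught anywhere?** Periods in which an extra hepatitis B dose could have been given, set against the rules:

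| Timing of extra dose | Entry criteria (Protocol 4.2, 4.3) | Protocol 10.4.3 |
|---|---|---|
| At birth | Excluded | Excluded |
| After birth, before first Infanrix hexa dose | Not named | Excluded |
| Between Infanrix hexa doses | Not named; arguably barred by the word consecutive | Excluded |
| After the fourth dose | Excluded | Excluded |

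The second row is open on any reading.

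**2. Does the replacement cohort close it?** SAP 5.1.2 requires that eligibility criteria are met, that procedures and intervals are followed, that no elimination criterion applies, and that Visit 2 results exist. Of the codes in SAP 5.2.2.1, 2010 covers violations of the entry criteria as written, 1040 covers forbidden concomitant vaccines, and 2060 and 2070 cover infections. The remaining codes concern consent, vaccine handling and administration, medication, medical conditions, sampling and data errors. None covers an earlier extra dose. The complementary TVC analysis in SAP 6.3.1 does not help, because the TVC would contain the same subjects.

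**3. How large could the effect be?** The plan gives no figure on this point. Inputs:
- Evaluable subjects: 300 × (1 − 0.10) = 270, as in Protocol 10.3.
- Base for persistence: 60%, from the statement in Protocol 1.2.1 that more than 60% were seroprotected in the earlier studies.
- Base for the primary endpoint: 94%, the lowest expected percentage in Table 16 (94.1% was observed at 12 to 13 years).
- Share f of subjects with an extra dose: not in the documents. Assumed range 1% to 5%.

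The worst case assumes that all such subjects are above the threshold when they would otherwise have been so at the base rate. Maximum rise in points = 100 × f × (1 − base).

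| f | Subjects (f × 270) | Persistence, base 60% | Primary endpoint, base 94% |
|---|---|---|---|
| 1% | 2.7 | 0.01 × 40 = 0.4 | 0.01 × 6 = 0.06 |
| 2% | 5.4 | 0.02 × 40 = 0.8 | 0.02 × 6 = 0.12 |
| 5% | 13.5 | 0.05 × 40 = 2.0 | 0.05 × 6 = 0.30 |

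The exact (Clopper-Pearson) 95% CI at 162/270 = 60% is 53.9% to 65.9%, so the worst shift is about a third of the distance from the estimate to either limit (2.0 against about 6). For the primary endpoint, even f = 5% converts 13.5 × 0.06 = 0.81 subjects, fewer than one. If the persistence base at 14 to 15 years were below 60%, the ceiling would be higher, but it can never exceed f itself, that is 1 to 5 points.

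**The case against.** The case for leaving the SAP alone is substantial, and most of it stands.

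- **The primary endpoint.** A reader might infer that the SAP stripped a safeguard from the post-challenge rate of 100 mIU/ml or more. It did not. Under Protocol 10.7 the rule in Section 10.4.3 applied to persistence only, and the cohort in Section 10.4.2 never contained it. Any gap on the challenge response dates from the protocol.
- **The width of the gap.** A reader might infer that any dose between birth and the fourth Infanrix hexa dose is admissible. The requirement for four consecutive doses can fairly be read as barring another hepatitis B vaccine between them. What clearly remains is the interval before the first dose.
- **Material bias.** Nothing in the documents shows that such histories occurred in this population, or how much one early dose would change antibody levels at 14 to 15 years. The range above is a bound under assumptions, not an estimate.
- **Disclosure.** SAP Section 9 lists the cohort removal as a major change and gives a reason. The other protections in Section 10.4.3 largely survive: age through code 2010, anti-HBc through code 2060, and birth doses and later boosters through the exclusions.

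What the objection does not answer is that the stated reason concerns cohort size, whereas what was lost is a condition defining the population. Similar numbers do not show that the same subjects qualify.

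**Conclusion.** The point holds for the persistence analysis. The SAP gave up the sponsor's own additional-dose rule without saying so, and neither the entry criteria nor the elimination codes replace it for a dose given after birth and before the first Infanrix hexa dose. The conclusion about the text needs no assumption about frequency.

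The numerical effect is probably small: at most 0.4 to 2.0 points on pre-challenge seroprotection and 0.06 to 0.30 points on the primary endpoint. Both ranges rest on an assumed 1% to 5% of subjects, bases of 60% and 94%, and every affected subject being above the threshold. SAP Section 7 makes every analysis descriptive, so no decision threshold is affected and no sample-size figure changes. This is a minor improvement in how the population is defined. It does not invalidate the analysis.

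**What to change.** Carry the condition from Protocol 10.4.3 into the cohort definition in SAP 5.1.2: no hepatitis B-containing vaccine other than the four Infanrix hexa doses and the study dose. Add it as an elimination condition in SAP 5.2.2.1, and report in the exclusion table how many subjects it removes. Because the SAP now uses one ATP cohort for both analyses, the condition would also apply to the primary endpoint, where the protocol did not have it. Record that in SAP Section 9.

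The cost is a line in each section and a check of vaccination histories already obtained at Visit 1, with no new procedure. The downside is that a few subjects may leave the ATP cohort. If none do, the report can say so and the estimates are unchanged.

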5. CONDUCT OF THE STUDY

5.1. Regulatory and ethical considerations, including the informed consent process

The study will be conducted in accordance with all applicable regulatory requirements.

The study will be conducted in accordance with the ICH Guideline for Good Clinical Practice (GCP), all applicable subject privacy requirements and the guiding principles of the Declaration of Helsinki.

The study has been designed and will be conducted in accordance with the ICH Harmonised Tripartite Guideline for clinical investigation of medicinal products in the paediatric population (ICH E11) and all other applicable ethical guidelines.

GSK will obtain favourable opinion/approval to conduct the study from the appropriate regulatory agency, in accordance with applicable regulatory requirements, prior to a site initiating the study in that country.

Conduct of the study includes, but is not limited to, the following:

- Institutional Review Board (IRB)/Independent Ethics Committee (IEC) review and favourable opinion/approval of study protocol and any subsequent amendments.
- Subject's parent(s)/LAR(s) informed consent and subject informed assent, as appropriate.
- Investigator reporting requirements as stated in the protocol.

GSK will provide full details of the above procedures to the investigator, either verbally, in writing, or both.

Freely given and written or witnessed/ thumb printed informed consent must be obtained from each subject's parent(s)/LAR(s) and subject informed assent, as appropriate, prior to participation in the study.

GSK Biologicals will prepare a model Informed Consent Form (ICF) which will embody the ICH GCP and GSK Biologicals required elements. While it is strongly recommended

that this model ICF is to be followed as closely as possible, the informed consent requirements given in this document are not intended to pre-empt any local regulations which require additional information to be disclosed for informed consent to be legally effective. Clinical judgement, local regulations and requirements should guide the final structure and content of the local version of the ICF.

In accordance with the ICH Harmonised Tripartite Guidelines for Good Clinical Practice, those subjects who can only be enrolled in the study with the consent of the subject's parent(s)/legally acceptable representative (e.g. minors), should be informed about the study to the extent compatible with the subject's understanding and, if capable, the subject should sign and personally date a written Informed Assent Form (IAF). It is required that the assent be signed by each subject, if capable, in addition to the informed consent that is to be signed by his/her legal representative.

The investigator has the final responsibility for the final presentation of the ICF and IAF, respecting the mandatory requirements of local regulations. The ICF and IAF generated by the investigator with the assistance of the sponsor's representative must be acceptable to GSK Biologicals and be approved (along with the protocol, and any other necessary documentation) by the IRB/IEC.

